5.6 Process Evaluation

We will determine whether the TEAM intervention was implemented as planned (**Aim 2**) and barriers/facilitators to implementation (**Aim 3**) to optimize the intervention for future dissemination. Mixed methods will be employed to obtain data on intervention implementation. We will capture data from 5 sources: 1) patients, 2) ACCESS EHR, and 3) pharmacies and staff.

Patients receiving the TEAM intervention will be asked to report whether they were contacted by Walgreens for a medication review and if it was useful (1-10 scale). Patients will be asked about their satisfaction with each aspect of the intervention (1-10 scale), whether they refused (yes/no) and why. If applicable, they will be asked if clinic staff contacted them to resolve regimen issues (yes/no) and to rate the quality of these interactions (1-10 scale; CAHPS).

Data from the EHR will be compared to determine whether adherence concerns were properly captured in the EHR (yes/no) and if a clinic response was documented (yes/no). Walgreens fill data will be utilized to document timeliness/completion of prescriptions.

We will conduct focus groups and/or individual interviews with up to 5 participating Walgreens pharmacists and pharmacy staff to explore barriers and facilitators to implementing the TEAM intervention. All focus groups/interviews will be audio-recorded and transcribed. All participants will give informed online consent prior to participation. We will pay pharmacists who complete these interviews \$150 in a Visa gift card sent a physical copy via mail or an electronic copy via email.

Cost Evaluation.

Throughout the trial, we will track explicit costs of implementing the TEAM intervention, from multiple sources (clinics, provider, community pharmacies, patient).

6.0 Data and Specimen Banking

Upon completion of all study activities, a final de-identified dataset will be created. This dataset will be stored indefinitely on the GIM server for secondary analyses. Only authorized personnel will have access to the dataset.

STU#: STU00209066

7.0 Sharing Results with Participants

Study results will not be shared with participants or anyone else.

8.0 Study Timelines

We anticipate the entire study will take 3 years to complete. The design phase will consist of a nine month window to finalize legal arrangements, an operational protocol and design and development of the evaluation tools. The implementation phase will occur between months 10-30. During this time, a brief pilot study (2-3 months) will finalize materials before the full implementation of the TEAM approach at ACCESS sites, recruiting 120 adults. Participants will be enrolled during a 20 month window and followed for a 12-month period. The evaluation phase will occur for the final 6 months of the study (months 31-36). During this time, quantitative and qualitative data will be collected from a variety of patient and provider sources to determine the extent to which the TEAM approach was delivered, as well as the impact on clinical workflow and patient outcomes.

Individual participants will be screened for eligibility (data pulls from ACCESS to identify new patients done on a quarterly basis) and if recruited and enrolled, will be active study participants for up to 6 months (baseline phone interview, TEAM intervention (if randomized to intervention arm) within 1 month of baseline, follow up phone interview at 2 months, potential TMR at 6 months), with a final EHR data pull completed 12 months post-baseline.

9.0 Inclusion and Exclusion Criteria

In order to participate in this study, patients must meet the following eligibility criteria:

9.1 Inclusion Criteria

Patients meeting inclusion criteria 1-5 below will be identified through ACCESS EHR data pulls on a quarterly basis. For those who qualify for the study based on these pulls, Northwestern RCs will contact these patients by phone to complete an initial phone screener during which time they will confirm criteria 1, 2, 5, and 6 as well as ensure that they do not meet any exclusion criteria.

- 1) Patient is age 50 and older
- 2) Patient is English or Spanish speaking
- 3) Patient has established care at one of the involved ACCESS health centers (defined as 1 visit within 18 months)
- 4) Patient is an existing Walgreens customer (had 1 or more medications filled at collocated Walgreens pharmacy within past 12 months)
- 5) Patient is currently prescribed 5 or more Rx medications (excluding antibiotics); that includes at least one medication from any of the following six therapeutic classes of medications: hyperlipidemia, hypertension, diabetes, multiple sclerosis, hepatitis C, and HIV
- 6) Patient is primarily responsible for administering own medication

9.2 Exclusion Criteria

We will further refine the list of eligible patients during the screening and consent process to exclude those with:

- 1) Severe, uncorrectable vision
- 2) Hearing impairments
- 3) Cognitive impairment (as measured by the 6-item screener)

STU#: STU00209066

10.0 Vulnerable Populations

Adults unable to consent and prisoners will be excluded from this research.

11.0 Participant Population(s)

Accrual Number:	Category/Group: (Adults/Children Special/Vulnerable Populations)	Consented: Maximum Number to be Consented or Reviewed/Collected/Screened	Enrolled: Number to Complete the Study or Needed to Address the Research Question
Local	120	120	120
Study-wide	120	120	120
Total:	120	120	120

12.0 Recruitment methods

12.1 Identification of potential participants

Prior to putting the intervention into production, providers and staff at all participating health centers will be oriented to the project. The study will be described to physicians at participating clinics. The Epic data pull will generate lists of their potentially eligible patients (by primary language, established ACCESS patient, age, # Rx taken, existing on-site Walgreens customer). Physicians will receive the list via an inbox message within the EHR; they will indicate if any identified patients should not be contacted. Patients deemed ineligible by providers will be removed from the list of patients to contact.

12.2 Recruitment procedure

Due to COVID-19, there need to be multiple recruitment methods in place in order to do what works best for ACCESS and their health centers, especially since research staff may still be working remotely and not logistically able to perform large recruitment mailings. Therefore, the two recruitment methods in place are recruitment calls and/or recruitment letters. For the first two weeks of the pilot, we will perform recruitment calls. We will reassess after two weeks to determine if we should continue with the recruitment calls or switch to mailing recruitment letters. Regardless of whether the initial patient recruitment occurs via phone or mail, all recruitment activities will be conducted by CITI-certified ACCESS and Northwestern Research Coordinators (RCs).

Recruitment Calls

An ACCESS RC will call patients identified through the Epic patient pull to read through the recruitment letter over the phone. The RC can also email a copy of the recruitment letter if the patient would like to review it. During the call, the RC will read a script that clearly explains that if they are interested, a RC from Northwestern will call them the following week to see if they are eligible for the study and to go through the consent form for this study at that time. The ACCESS

STU#: STU00209066

RC will obtain verbal permission from the patient to allow a RC from Northwestern to contact them about the research study.

If the patient answers and agrees to being contacted by the Northwestern RC, the ACCESS RC will add that patient to the list that will be sent to NU. If the patient answers and would like to opt out, the ACCESS RC will remove the patient from the list. If the patient does not answer, the RC will leave a voicemail for the patient. The ACCESS RC will make up to four attempts by phone to recruit the patient before categorizing them as a passive refusal and removing them from the patient list.

At the end of the week, the ACCESS RC will send a list of patients that agreed to be contacted to Northwestern. The Northwestern RC will then screen the patient to determine eligibility (English or Spanish-speaking, responsible for administering medication regimen, taking 5+ medications, prescribed at least one medication from any of the selected six therapeutic classes (confirmed via brief chart review), no severe cognitive, hearing, visual impairment). If eligible, the RC will obtain informed online or verbal consent at the end of the call. If the patient is unable to stay on the phone to consent, the RC will schedule a follow up call to consent the patient before the baseline will be done. During the screening and consent call, the Northwestern RC will schedule the call to conduct the baseline assessment and randomize the patient to study arm. Prior to the baseline interview, the Northwestern RC will conduct a more thorough review of the patient medication list through either receiving a file from ACCESS or through read ability in EPIC for patient charts.

Recruitment Letters

An ACCESS RC will mail a letter to patients remaining on the list, notifying them that a RC from Northwestern University will be phoning to invite them to participate in a study. Patients will have the opportunity to opt out of being contacted. Ten days after the mailing, the Northwestern RC will start to contact patients by phone to ask if they would be interested in participating. If interested, the RC will screen the patient to determine eligibility (English or Spanish-speaking, responsible for administering medication regimen, taking 5+ medications, prescribed at least one medication from any of the selected six therapeutic classes (confirmed via brief chart review), no severe cognitive, hearing, visual impairment). If eligible, the RC will obtain informed online or verbal consent at the end of the call. If the patient is unable to stay on the phone to consent, the RC will schedule a follow up call to consent the patient before the baseline will be done. During the screening and consent call, the Northwestern RC will schedule a phone interview to conduct the baseline assessment and randomize the patient to study arm. Prior to the baseline interview, the Northwestern RC will conduct a more thorough review of the patient medication list through either receiving a file from ACCESS or through read ability in EPIC for patient charts.

Training will begin after questionnaire and interview protocols have been refined and standardized. The PIs and project manager will lead sessions to orient the research staff to the surveys and study protocols (e.g., interview process, use of laptop PCs, data security). All interviewers will be required to demonstrate competence in survey administration. All interviews will be conducted via REDCap, a secure, web-based application. Recruitment outcomes along with identifiable data necessary to contact participants will be recorded in NU's REDCap. Interviews will be conducted by research coordinators (RCs) over the phone. RCs will read each question aloud and record patient

STU#: STU00209066

responses directly onto a password protected laptop or PC computer using REDCap. Study interview data does not contain any identifiable information, and are identified by project staff by an assigned study ID. All identifiable information will remain in the secure REDCap system. Contacts with enrolled participants will be made via email, USPS and telephone.

13.0 Compensation for Participation in Research Activities

Patients will receive incentives for study visits (\$50 gift card or money order for baseline and a \$50 gift card or money order for 2 month follow up phone call). Compensation will be mailed to the patient's home address.

14.0 Withdrawal of Participants

In the case that subjects are unresponsive for 6 months past the date their follow up interview was due, they will be labeled as 'lost to follow up' and will be withdrawn from the study.

Participants can choose to withdraw from the study at any time. If a participant chooses to withdraw from the research, any data collected up until the point of withdrawal will still be utilized as it will not include identifying information.

15.0 Risks to Participants

Participation in the study poses minimal risk of psychological, social and economic harm. Informing subjects in advance that they may decline to answer any questions asked during the interview and discussion group will mitigate any risks associated with expressing their opinions (e.g., feeling uncomfortable). They will also be assured they can terminate their participation in the study at any time without penalty. The risk/benefit ratio is low. Minimal to no risk is expected for subjects in this study.

16.0 Potential Benefits to participants

It is possible that subjects enrolled in the intervention study arms may directly benefit in that they may have, as a result of this study, a better functional understanding of their medication. The results of this study may provide important information regarding how strategies can be implemented via the EHR and enhanced provider and pharmacist communication to support safe and appropriate medication use.

17.0 Data Management and Confidentiality

17.1 Analysis Plan

All analyses will be performed in SAS v9.4 (SAS Institute, Cary, NC). [name] will perform analyses under the direct supervision of [name] and Drs. [name] and [name].

Aim 1. Evaluate the fidelity and efficacy of the TEAM intervention to promote healthcare provider counseling, medication reconciliation, and safe regimen use among adults taking complex Rx regimens.

Quantitative analyses will be performed using SAS v9.4 (SAS Institute, Cary, NC). To ensure adequate balance across treatment arms, baseline outcomes and potential confounders including socio-demographic characteristics, comorbidities, regimen complexity, health literacy

STU#: STU00209066

level will be compared using ANOVA models and χ^2 tests, as appropriate. Variables found to have significant differences ($p < .05$) across treatment groups will be entered as covariates in the generalized linear mixed models (GLMMs) used for formal analyses as described below. Treatment arm will serve as the primary independent variable. Analyses will be performed using PROC GLMMIX in SAS (v.9.4). A binary variable will be included in the model to denote the intervention group vs. usual care. As we will use stratified randomization by site, we will include in the GLMM an indicator variable for site and any potential confounding covariates noted in the descriptive studies. For outcomes assessed for each medication, 2-level GLMM will be used with medications nested in participants. Additionally, as there may be some effect of provider on adherence, we will explore the effect of any PCP by including provider as a random-effect. Using similar models as described above, we will assess the impact of TEAM on clinical markers (HbA1c, blood pressure, cholesterol) among patients with diabetes and hypertension.

Aim 2. Explore patient, healthcare provider (pharmacist, prescriber), community pharmacy and/or primary care practice barriers to implementation.

We will determine the extent to which the TEAM intervention was implemented as planned at each site in order to optimize the intervention for future dissemination opportunities. Mixed methods will be employed using a convergent parallel design to obtain data on intervention implementation. Quantitative and qualitative findings will be synthesized together to yield a more comprehensive understanding of: 1) whether the interventions were implemented as planned; 2) if (and how) the TEAM intervention might be modified based on user feedback. In this approach, both analyses are conducted separately and synthesized for side-by-side data comparisons. For quantitative data (patient report, EHR, pharmacy data), frequencies will be generated to determine outcomes related to receipt of notifications and feedback and perceived helpfulness of TEAM processes. Similar GLM models as described in Aim 1 analyses will be performed, with TEAM intervention arm as the primary independent variable.

For qualitative data, the study team will review common themes found throughout the pharmacist interviews drawn from the discussion guide and the pharmacists responses. We will use an iterative approach to identify and group emergent themes. Pharmacist quotes will be identified to highlight themes. Attention will be paid to facilitating factors and impeding factors identified during the interviews. An additional layer within impeding factors would be whether or not factors are modifiable, and under facilitating factors, if they are replicable.

Aim 3. Determine the costs of the TEAM intervention from both a community pharmacy and primary care practice perspective.

We will directly measure and assess the costs of developing and running the TEAM intervention. The incremental cost of both strategies will be estimated relative to usual care and each other from both the perspective of the FQHC sites and the Walgreens pharmacies delivering the MTM services. The primary resources for running TEAM include from pharmacy: 1) Walgreens pharmacist time for contacting patients, conducting medication reviews, documentation, messaging prescribers; 2) Walgreens clinical analyst to program adherence reports. Resources to implement TEAM from the primary care practice include: 3) discrete ACCESS programming time for linking Walgreens pharmacies with read/write access; 4) clinic orientation to the newly-available TEAM process and available safety alerts and adherence data, and training on how to respond. The costs of the pharmacist, analyst time (for both ACCESS and Walgreens) are easily

STU#: STU00209066

documented. For costs associated with staff training, estimates will be made, with sensitivity analyses performed assuming orientations performed by staff at varying levels of experience based on internal data on wages as well as nationally representative estimates from the Bureau of Labor Statistics.

We will also include estimates for the cost of programming maintenance at each site for the Epic EHR, testing the sensitivity of results to changes in maintenance requirements (in programmer hours) along with internal data on wages. Costs associated with diverted time and changes to workflow to attend to alerts and messages from the pharmacist will also be estimated, as well as changes in the efficiency within a pharmacy due to more rapid communication channels with prescribers. Development costs for software and other programming will be separately tracked. Staff/programmer costs will be measured using tracked time spent on the intervention and wage estimates. We will test the sensitivity of operational costs to different assumptions about potential use of variable staff using different salaries but assuming the same proficiency in time required. We will also assess the sensitivity of estimates to different proficiency levels that could arise from learning by doing.

17.2 Protocol to ensure confidentiality.

Each subject will be tracked using an Access database. The database, containing identifiers and other related information for coordinating research activities (recruitment outcome, interview call log and interview visit schedule, etc.) will be kept on the secure Northwestern network drive. Only the PI, project manager, and RC will have access to this database. ACCESS participants will be additionally tracked in their EPIC EMR system, only accessible by ACCESS study personnel.

Data will be collected via REDCap. REDCap is a secure, encrypted online data collection tool, which can only be accessed by NU authorized personnel listed on the project's IRB.

Several methods will be employed to reduce the risk of breach of confidentiality. A study identification number will be assigned to each subject in the study. The research data collected and stored will have the study identification number and no other identifying information on it. The de-identified study data will be kept in a separate locked file cabinet. Using this method, if someone were to gain illegal access to the locked filing cabinet with study data, they would have no way to link this data to any identifying information.

17.3 Quality Assurance.

Training will begin after surveys and interview protocols have been refined and standardized. A training session will be conducted by Drs. [name] and [name]. The training will include tailored discussion of 1) roles and responsibilities; 2) HIPAA and IRB mandates (completion of Human Subjects Training Program - CITI; 3) effective recruitment communication and interviewing with attention paid to health literacy and culture; and 4) gathering and recording data including administering the structured survey electronically. Role playing will be used to fine tune training for obtaining informed consent and interviewing patients. Institutional Review Board (IRB) approval will be attained at both sites prior to any active recruitment efforts. All interviewers will be required to demonstrate competence in survey administration.

STU#: STU00209066

17.4 Study-wide data management.

Data collected includes patient consent forms, data gathered using the ACCESS patient lists, and data collected during the study interviews.

Data Access. The Data Custodian is the Principal Investigator, [name]. Only authorized personnel listed on each institutions IRB will have access to the data. Any information that could allow identification of individual participants, including the master list, will be kept strictly confidential.

Local Data Storage. Data will be stored in REDCap, a secure, web-based application, and on the Northwestern secure server for the length of the study. The Project Manager or Data Analyst will download the de-identified data only from REDCap monthly and save to the “Analytic” folder within the TEAM project folder on the FSM department servers which are located in a HIPAA compliant data center. These data files do not contain any identifiable information, and are identified by project staff by an assigned study ID. All identifiable information for ACCESS patients will remain in the secure REDCap system. Upon completion of all study activities, a final de-identified dataset will be created and all identifiable information will be deleted. This dataset will be stored indefinitely on the GIM server for secondary analyses. Only authorized personnel will have access to the dataset. All identifiable information will be deleted upon completion of the study

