4.2 Medication Review by Telephone

The Walgreens Research Analytics Team will be notified of all patients randomized to the TEAM intervention on a weekly basis. They will then generate an Adherence Report for all medications in the predetermined six therapeutic medication classes, which will include rolling 12 month PDC per medication. This Adherence Report will be sent directly to the Walgreens pharmacist prior to initiating the CMR by phone. S/he will retrieve contact information for the patient via the EHR and attempt to initiate an introduction via telephone, wherein the pharmacist will explain his/her role, and establish a time (on the introductory call or scheduled for a later date) to perform a medication review. This is estimated to take between 10-45 minutes, depending on the size and complexity of the patient's regimen. The pharmacist will begin by reconciling the Epic EHR medication list with the patient, matching up what the patient is currently taking, what has been discontinued by a prescriber, what is still prescribed but the patient is not taking (and why), and identifying any omissions. Each medication will be reviewed, either in the list or identified by the patient, including a brief review of how patients take the medicine to ensure safe use. Patients will also be probed on whether they are experiencing any symptoms that could be signs of an adverse drug event (ADE). Pharmacists will address any questions or concerns patients may have about their medicine (e.g. side effects, treatment alternatives, dietary restrictions, cost, 90 vs. 30 day scripts), and assess patients' adherence. If missed doses or premature discontinuation is reported, problems (e.g. cost, forgetfulness) will be discussed and assistance offered (e.g. synchronization requests, pill box, reminders).

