5.2 Phases of the Project

The following activities will be performed during the proposed project, by phase:

Design Phase (months 1-9)

1. Organize Northwestern-Walgreens-ACCESS team; establish project milestones, roles.
2. Convene all stakeholders (primary care providers, Walgreens pharmacists and leadership) to gather feedback on the initial draft standard operating protocol (SOP) for the implementation of TEAM in ACCESS clinics, leveraging Walgreens pharmacists will be developed. This is an iterative process with all TEAM users.
3. Amend existing Walgreens-ACCESS agreements to include new Epic read/write access, given the parameters established by the mutually-agreed upon SOP. This includes the specification of set security points within the ACCESS EHR (Epic) that both allows and controls pharmacist permissions. Our Northwestern team has already worked with ACCESS and Walgreens to detail the TEAM protocol (see section 4.0 study intervention).
4. Devise an implementation evaluation battery capturing process outcomes and also a range of patient-reported medication safety-related outcomes.

Implementation phase (months 10-30)

5. 'Beta test' the TEAM strategy in the clinical environment to confirm the functionality of all bi-directional information sharing components.
6. Trouble shoot any technical/procedural concerns, modifying the SOP accordingly.
7. Orient participating ACCESS clinical sites and Walgreens staff on the final SOP in preparation for the live implementation to be conducted in the second project phase.
8. Implement the finalized TEAM intervention protocol defined in the Design Phase at ACCESS clinic sites. The strategy includes Walgreens pharmacist outreach with identified

STU#: STU00209066

ACCESS patients to: a) perform medication reviews, b) generate automatic and tailored EHR-based alerts; c) provide clinical decision support.

9. Enroll 120 patients into the pilot study.
10. Randomize patients (1:1) to either: 1) the TEAM intervention or 2) enhanced usual care.
11. Conduct baseline (by phone) and 2 month follow-up interview (by phone) with enrolled patients. Interviews will include validated measures and will be completed using RedCAP software for data quality and safety. Data will also be abstracted from patient EHR records at 12 months post-enrollment.

Evaluation Phase (months 31-36)

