We will ask patients (yes/no) whether their prescriber/nurse/pharmacist counseled them about their medications. We will also ask the Health Literacy supplemental items of the Consumer Assessment of Health Providers Survey (CAHPS) to evaluate the extent and quality of provider verbal counseling on Rx medications.

For the outcomes described below, we only include chronic Rx medications. Though we document them, we exclude PRN or limited duration drugs, as adherence concerns are different. All of these measures have been used in multiple studies by our team; results have been published extensively.

Medication Reconciliation

At each interview, commissions (medications listed in the EHR and the patient reported not taking) and omissions (patient reported medications not in the EHR) will be calculated based on medication lists and patient self-report.

Medication knowledge. Medication-specific knowledge will be measured through a series of open-ended questions, capturing patients' knowledge of each of their medication's: 1) indication for use and 2) risks, warnings or potential side effects. Answers will be qualitatively reviewed and independently scored as correct/incorrect by two RCs according to medication information provided from ACCESS and Walgreens. For any that the RCs do not have information on or any with discordance between RCs, a pharmacist will qualitatively review and independently score as correct/incorrect.

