Medication dosing errors. We will use a 24-hour recall procedure utilized extensively by this team in prior and current studies to assess Rx dosing errors. At each interview, RCs will review medications reported as taken by the patient and those listed in the EHR to create a final list of medications prescribed to the patient. RCs will then ask patients to report, one by one, how they took each medication over the past 24 hours. Patients will be asked to specify the amount taken (i.e. dose) and when taken (to determine frequency and interval between doses). Patients will be asked to report whether this was how the medication was prescribed, and if not, will be queried: 1) to determine the reason for not taking the medication as prescribed (i.e. forgetfulness, ran out of medication) and 2) to describe how the medication *should* be taken. Data from this exercise will be used to assess correct dosing (yes/no) based upon the instructions for each medication. It will also be used to calculate regimen consolidation, or the total number of time points throughout the 24-hour period that a patient reported taking one or more medicines (count variable, range: 1-24).

Medication adherence. Adherence will be measured using: 1) the Ask-12 survey and 2) the proportion of days covered (PDC) according to pharmacy records. The Ask-12 is a brief measure of adherence that covers three domains: inconvenience/forgetfulness, treatment beliefs and behavior. In prior studies, the tool demonstrated good internal consistency reliability (Cronbach's α 0.75) and test-retest reliability (intraclass correlation 0.79); convergent validity was also

STU#: STU00209066

demonstrated through correlations with multiple other measures (Morisky, SF-12) and pharmacy claims data. Ask-12 scores range from 12-60, with higher scores indicating poorer adherence. PDC will be calculated by summing the number of days' supply obtained by a patient during a given time period and dividing by the number of days for which the medication was prescribed. For each patient, we will assess adherence within drug class. If a patient fills a prescription for a drug and switches to another drug within the same class, all prescriptions will be summed in the numerator. Adherence will be treated continuously and dichotomously (yes/no; PDC at disease-specific threshold based on Pharmacy Quality Alliance (PQA) standards). PDC data will be automatically obtained from Walgreens as part of the TEAM study.

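### Apart from site, Aim 1 covariates, including each outcome's own baseline value, enter the model only if a between-arm baseline test gives p<.05, so the baseline value is dropped about 95% of the time and precision is lost

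*Combined protocol and SAP*

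**What the plan says.** Section 17.1, Aim 1, begins with a between-arm comparison by ANOVA and chi-square tests. The variables compared are "baseline outcomes and potential confounders including socio-demographic characteristics, comorbidities, regimen complexity, health literacy" level. The rule that follows is: "Variables found to have significant differences ($p < .05$) across treatment groups will be entered as covariates" in the generalised linear mixed models.

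Arm is the main independent variable. Site is the only other unconditional term: "As we will use stratified randomization by site, we will include in the GLMM an indicator variable for site". The same sentence adds confounders noted in the descriptive step, which points back to the comparison just described. Medications are nested in participants for medication-level outcomes, and a provider random effect is exploratory. The section describes no time term, arm-by-time term or change score, and no repeated-measures model.

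Baseline values of the interview outcomes will exist. Section 5.2 plans interviews at baseline and 2 months. Section 5.5 has reconciliation recorded both times: "At each interview, commissions (medications listed in the EHR and the patient reported not taking) and omissions (patient reported medications not in the EHR"). The 24-hour dosing recall is also done at each interview. Section 5.4 randomises patients 1:1 within site, 60 per arm.

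**The concern.** In an individually randomised trial a baseline difference between arms is chance. Testing it shows nothing about whether a variable is worth adjusting for. The reason to adjust is that the variable predicts the outcome, and an outcome's own baseline value is often its strongest predictor. The rule selects on the chance imbalance instead, so it nearly always leaves that predictor out, and it can give different outcomes different covariate sets for no substantive reason.

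At stake is the precision of the Aim 1 comparisons. With at most 60 patients per arm, information the interviews already collect is set aside, and a real effect on a continuous outcome is more likely to be missed.

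**Working it through.** The documents give no power calculation, effect size, standard deviation or dropout rate, so there is no stated figure to reproduce. The only check is 120/2 = 60 per arm, which agrees.

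**Inputs from the documents.** 60 per arm, 1:1 (5.4); entry threshold p<.05 (17.1); ASK-12 "test-retest reliability (intraclass correlation 0.79") from prior studies (5.5). The last is used here as an upper bound for the baseline to follow-up correlation r.

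**Assumptions.** Continuous outcome, two-sided 5% test, effect 0.4 SD, r = 0.3, 0.5 or 0.7.

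**Step 1: how often the baseline value is left out.** Under randomisation the baseline null hypothesis is true, so P(p ≥ .05) = 1 − 0.05 = 95%. In simulation the baseline value was selected in 4.8% to 5.1% of trials.

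**Step 2: what is lost.** Unadjusted, the SD of the estimate is √(2/60) = 0.183 SD. Adjusting for baseline multiplies it by √(1 − r²). The number of patients giving the same precision without adjustment is 120/(1 − r²):
- r = 0.3: 120/0.91 = 132
- r = 0.5: 120/0.75 = 160
- r = 0.7: 120/0.51 = 235
- r = 0.79: 120/0.376 = 319

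**Step 3: the rule itself.** 40,000 simulated trials per setting, bivariate normal baseline and follow-up, effect 0.4 SD (type I error simulated at zero effect):

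| r | Power, never adjusted | Power, p<.05 rule | Power, planned adjustment | SD of estimate, rule / planned | Type I error, rule |
|---|---|---|---|---|---|
| 0.3 | 58.7% | 59.0% | 62.5% | .180 / .175 | 4.7% |
| 0.5 | 58.3% | 59.0% | 70.0% | .177 / .159 | 4.5% |
| 0.7 | 58.3% | 60.0% | 85.8% | .170 / .131 | 3.5% |
| 0.79 | 58.4% | 60.5% | 94.3% | .166 / .112 | 3.1% |

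The rule performs almost like never adjusting. Its mean bias is at most 0.002 SD. Type I error with planned adjustment is 4.9% to 5.1%.

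**Step 4: sensitivity.**
- Effect 0.5 SD: rule against planned is 77% vs 81% (r = 0.3), 79% vs 88% (0.5) and 80% vs 97% (0.7).
- Assumed 15% loss to follow-up (60 × 0.85 = 51 per arm), effect 0.4 SD: 51.9% vs 55.1%, 52.2% vs 63.3%, 53.5% vs 79.7% and 53.5% vs 89.8% for the four values of r.
- Weak correlation, 0.4 SD, 60 per arm: 58.5% vs 58.6% at r = 0.1 and 58.5% vs 59.9% at r = 0.2.

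**Step 5: imbalances the screen misses.** The test triggers at 1.98 × 0.183 = 0.362 SD. A gap of 0.20 to 0.362 SD occurs in 22.6% of randomisations and goes unadjusted. It shifts the estimate by r times the gap: 0.5 × 0.20 = 0.10 to 0.5 × 0.362 = 0.18 SD at r = 0.5. This is the same lost precision seen within a single trial, not a second cost.

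**Step 6: yes/no outcomes.** The variance formula does not carry over. For one yes/no answer per patient (assumed 50% vs 70%, logistic model, 8,000 trials), power is 61.6% vs 64.4% at a baseline to follow-up phi of 0.3 and 62.7% vs 72.5% at 0.5. The log-odds standard error rises with adjustment (.387 to .413 and .461), so the benefit there is power, not a narrower interval.

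**The case against.** Several points on the other side are fair.

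- **The 95% assumes a valid participant-level test.** Section 17.1 does not say at which level the screen runs. If medication-level baselines were tested with plain ANOVA or chi-square, clustering would raise the trigger rate. With an assumed 5 to 8 medications and intraclass correlation 0.1 to 0.3, the design effect 1 + (m − 1) × ICC runs from 1.4 to 3.1, the trigger rate from 10% to 27%, and exclusion from 90% down to 73%. This stands as a caveat, but entry driven by an invalid test is no defence of the rule.
- **The size rests on assumptions.** Only 0.79 is in the protocol. It concerns one scale, so the r = 0.7 and 0.79 rows should not be read as typical. Single-day recall may correlate weakly. The gain is small at r = 0.3 and negligible near zero, though planned adjustment cost no power there either.
- **The simulations do not cover every outcome.** Discrepancy counts and per-medication yes/no outcomes were not simulated.
- **Outcome-driven selection is not the issue.** The threshold is fixed in advance, uses baseline data only, and Section 5.4 blinds the analysts. What remains is that the covariate set is unknown until the arms have been compared.
- **It is a pilot with no power target.** True, but Aim 1 is to evaluate efficacy and 17.1 treats these models as the formal analyses. A small trial also gains most from narrower intervals.

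**Conclusion.** The concern holds. As written, each outcome's own baseline value is left out of the Aim 1 model about 95% of the time under a valid participant-level screen, and the rule recovers almost none of the precision available.

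For a continuous outcome with 60 per arm, the SD of the estimate under planned adjustment is 3%, 10%, 23% and about 32% smaller than under the rule at r = 0.3, 0.5, 0.7 and 0.79. At an assumed 0.4 SD effect and r = 0.5 this is 11 percentage points of power. The figures depend on r and the effect size, neither of which the protocol supplies for its outcomes.

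Validity is not in question: the estimate is unbiased on average and the test is conservative. This is an avoidable inefficiency that should be corrected before the analysis.

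**What to change.** In Section 17.1, delete the p<.05 entry rule and keep the baseline table as description. Then state:

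- Each Aim 1 model for an outcome measured at the baseline interview includes that participant's baseline value and the planned site indicator. For medication-level outcomes, use the participant's baseline proportion.
- Any further covariates, such as regimen complexity or health literacy, are fixed before unblinded analysis.
- Proportion of days covered and clinical markers are adjusted for the pre-baseline value where the pharmacy or EHR extract supplies it in both arms.
- Missing baseline values follow a stated rule, for example the mean over both arms plus a missing indicator.

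The cost is wording and about one model degree of freedom per outcome, with no new interview data. The pharmacy and EHR extracts may need a small addition to the data request. The 12-month adherence report in Section 4.2 is described only for the intervention arm: "The Walgreens Research Analytics Team will be notified of all patients randomized to the TEAM intervention on a weekly basis". Section 5.5 does plan adherence data from the pharmacy for the study without limiting it to one arm, so the point there is to confirm that the window reaches back before baseline. For clinical markers, Section 5.2 says "Data will also be abstracted from patient EHR records at 12 months post-enrollment" and does not state whether that pull covers pre-baseline values.
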